4.4.1.2.4 Duration

Duration is derived from the start and stop dates of the unsolicited non-serious AE provided in the clinical database:

- stop date of unsolicited non-serious AE - start date of unsolicited non-serious AE + 1.

The duration should be considered as missing only if one or both of the start and stop dates of the unsolicited non-serious AE is missing or partially missing.

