**9.3.1.3.3 Unsolicited Non-serious Adverse Events From D0 to V02 After Vaccination**

In addition to recording solicited reactions, subjects or subjects' parents/guardians will be instructed to record any other medical events that may occur between V01 and V02. Space will be provided in the DC for this purpose. For each unsolicited non-serious AE, the following information is to be recorded:

- Start and stop datesb
- Intensity of the event:
  - For measurable unsolicited non-serious AEs that are part of the list of solicited reactions, the size of the AE as well as the temperature for fever will be collected and analyzed based on the corresponding scale used for solicited reactions (see [Table 9.1](#) and [Table 9.2](#)).

---

a Regardless of the arm circumference measurements and differences, if in the subject's or subject and their parent/guardian opinion the subject develops ELS of the vaccinated arm during the 7 day period after vaccination, the subject or subject and their parent/guardian is required to contact the site immediately on the same day the ELS is observed

b The stop date of all related AEs will be actively solicited. For other events, the investigator will provide the stop date when it becomes available. AEs for which no stop date was obtained during the course of the study will be considered as ongoing at the end of the study.

- Other unsolicited non-serious AEs will be classified according to the following intensity scale:
  - Grade 1: No interference with activity
  - Grade 2: Some interference with activity
  - Grade 3: Significant; prevents daily activity
- Action taken for each AE, if any (e.g., medication)

The action taken by the subjects or subjects' parents/guardians to treat any **unsolicited AEs** will be classified in the eCRF using the following scale:

- 0: None
  - 1: Medication (self-medication with an existing prescription or over-the-counter medication)
  - 2: Health care provider contact (no new medication prescribed)
  - 3: Health care provider contact and prescription of a new medication (health care provider instructed subject to take a new medication, either an over-the-counter medication or one requiring a written prescription)
- Whether the AE led to discontinuation
  - Whether the AE was related to vaccination (for unsolicited systemic AEs)

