4.3.1.3.3 Unsolicited Non-serious Adverse Events From D0 to V02 After Vaccination

In addition to recording solicited reactions, subjects or subjects' parents/guardians will be instructed to record any other medical events that may occur between V01 and V02. Space will be provided in the DC for this purpose. For each unsolicited non-serious AE, the following information is to be recorded:

- Start and stop dates⁷
- Intensity of the event:
 - For measurable unsolicited non-serious AEs that are part of the list of solicited reactions, the size of the AE as well as the temperature for fever will be collected and analyzed based on the corresponding scale used for solicited reactions (see Table 4.1 and Table 4.2).

⁶ Regardless of the arm circumference measurements and differences, if in the subject's or subject and their parent/guardian opinion the subject develops ELS of the vaccinated arm during the 7 day period after vaccination, the subject or subject and their parent/guardian is required to contact the site immediately on the same day the ELS is observed

⁷ The stop date of all related AEs will be actively solicited. For other events, the investigator will provide the stop date when it becomes available. AEs for which no stop date was obtained during the course of the study will be considered as ongoing at the end of the study.

- Other unsolicited non-serious AEs will be classified according to the following intensity scale:
 - Grade 1: No interference with activity
 - Grade 2: Some interference with activity
 - Grade 3: Significant; prevents daily activity
- Action taken for each AE, if any (e.g., medication)

The action taken by the subjects or subjects' parents/guardians to treat any **unsolicited AEs** will be classified in the eCRF using the following scale:

- 0: None
 - 1: Medication (self-medication with an existing prescription or over-the-counter medication)
 - 2: Health care provider contact (no new medication prescribed)
 - 3: Health care provider contact and prescription of a new medication (health care provider instructed subject to take a new medication, either an over-the-counter medication or one requiring a written prescription)
- Whether the AE led to discontinuation
 - Whether the AE was related to vaccination (for unsolicited systemic AEs)

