4.3.1.3.7 Assessment of Causality

The Investigator will assess the *causal relationship* between each unsolicited systemic AE and vaccination as either not related or related, based on the following definitions⁸:

- 0: Not related – The AE is clearly / most probably caused by other etiologies such as subject’s underlying condition, therapeutic intervention, or concomitant therapy; or the delay between vaccination and the onset of the AE is incompatible with a causal relationship; or the AE started before the vaccination (screening phase, if applicable)
- 1: Related – There is a “reasonable possibility” that the AE was caused by the vaccination, meaning that there is evidence or arguments to suggest a causal relationship

Note: By convention, all injection site AEs (solicited and unsolicited) and all solicited systemic reactions are considered to be related to vaccination and referred to as reactions, and therefore do not require the Investigator’s opinion on relatedness.

AEs likely to be related to the product, whether serious or not, that persist at the end of the trial will be followed up by the Investigator until their complete disappearance or the stabilization of the subject’s condition. The Investigator will inform the Sponsor of the date of final disappearance of the event.

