4.4.1.3.3 Duration

Duration will be computed using the same methodology than for unsolicited non-serious AEs described in [Section 4.4.1.2.4](#).

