5.1.3.2.2 Safety

The number and percentage of subjects reporting any solicited injection site reactions and solicited systemic reactions will be summarized by study group, intensity (Grade 1, Grade 2, and Grade 3), and period (D0 to D3, D4 to D7, and D0 to D7 after vaccination) for each reaction term. For a time period in which more than 1 intensity was recorded, the highest intensity will be used. Exact (Clopper-Pearson) 2-sided 95% confidence intervals (CIs) will be calculated for the percentages.

Immediate reactions, unsolicited AEs (including MAAEs), and SAEs will be coded and presented by MedDRA preferred term and system organ class (SOC). The number and percentage of subjects reporting safety findings will be summarized by study group for each preferred term, and SOC that has at least 1 report, as well as by relationship to study vaccine. SAEs will be tabulated separately from D0 through the end of the 6 month follow-up. Unsolicited AEs representing a change in the health status of the subject will be presented from D0 through D30. MAAEs will be presented from V01 through V02 through the end of the 6-month follow-up period.

Descriptive statistics will include, but not be limited to:

Table 5.1: Statistical analyses for safety observational objective

Safety Events	Time and Group	Description
Immediate unsolicited systemic AE	Within 30 minutes after injection for all subjects in Groups 1 - 6 at D0	Percentage of subjects that have the event, MedDRA terms, intensity, relationship to vaccine, study discontinuation, duration
Extensive limb swelling	Up to 7 days after D0 for all subjects in Groups 1 – 6	Percentage of subjects that have the event
Solicited injection site reactions	Up to 7 days after D0 for all subjects in Groups 1 – 6	Percentage of subjects that have the event, time of onset, duration, intensity, action taken, study discontinuation, number of days of occurrence
Solicited systemic reactions	Up to 7 days after D0 for all subjects in Groups 1 – 6	
Unsolicited AE	Up to 7 days after D0 for all subjects in Groups 1 – 6 From D0 to D30 for all subjects in Groups 1 – 6	Percentage of subjects that have the event, MedDRA terms, time of onset, duration, intensity, relationship, action taken, study discontinuation

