SAE	Up to 7 days after D0 for all subjects in Groups 1 – 6 From D0 to D30 for all subjects in Groups 1 – 6 From D31 to 6-month follow-up contact for all subjects in Groups 1 – 6 Up to 6-month follow-up contact after D0 for all subjects in Groups 1 – 6	Percentage of subjects that have the event, MedDRA terms, time of onset, duration, relationship, seriousness criteria, outcome, study discontinuation
MAAE	From V01 to V02 for all subjects in Groups 1 - 6 (as unsolicited AE) From V02 to 6-month follow-up contact for all subjects in Groups 1 - 6	Percentage of subjects that have the event, MedDRA terms, time of onset, duration, intensity, relationship, action taken, outcome, study discontinuation

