5.3.1.5 Start Date and Stop Date

Missing or partially missing start dates for unsolicited non-serious AEs will remain missing and not be imputed. If the start date is missing or partially missing, the time of onset will be considered to be missing. Nevertheless unsolicited AEs with missing time of onset will be included in analyses according to the visit collected.

Since SAEs are not collected by visit, though missing or partially missing start dates will not be imputed, logic will be applied to determine whether the event started between D0 to D30 or between D31 to 6-month follow-up contact.

Missing or partially missing stop dates for AEs (solicited reactions and unsolicited AEs) will remain missing and not be imputed.

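### AE duration is set to missing when an event has no stop date, so unresolved events drop out of the duration summaries and reported durations lean short

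*SAP*

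**What the plan says.** For unsolicited non-serious AEs, SAP 4.4.1.2.4 computes duration as stop date minus start date plus 1. It then adds: "The duration should be considered as missing only if one or both of the start and stop dates" are missing or only partly known. SAP 4.4.1.3.3 extends this to SAEs: "Duration will be computed using the same methodology than for unsolicited non-serious AEs". SAP 5.3.1.5 closes the alternative: "Missing or partially missing stop dates for AEs (solicited reactions and unsolicited AEs) will remain missing and not be imputed".

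Both documents also say what an absent stop date means. Protocol 9.3.1.3.3 (footnote b), repeated in footnote 7 of SAP 4.3.1.3.3, reads: "AEs for which no stop date was obtained during the course of the study will be considered as ongoing" when the study ends. The same footnote says of related events: "The stop date of all related AEs will be actively solicited". For other events the investigator supplies the date once it is available.

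Duration is a component of the endpoints for unsolicited AEs, SAEs and MAAEs (Protocol 9.3.1.2, SAP 4.3.1.2) and an output for all three in SAP Table 5.1. For unsolicited AEs that table lists "MedDRA terms, time of onset, duration, intensity, relationship, action taken, study discontinuation". For SAEs it lists "MedDRA terms, time of onset, duration, relationship, seriousness criteria, outcome, study discontinuation". The MAAE row also includes outcome; the unsolicited AE row does not.

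**The concern.** An event that starts on a known date and has not ended at last contact does not have an unknown duration. It has lasted at least from onset to last contact. The derivation ignores the ongoing status that the SAP itself assigns and treats the event as if nothing were known about its length.

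Whether a stop date is absent depends on how long the event lasts, so the deletion is informative. A summary over the remaining events describes resolved events only. The study is descriptive, so no error rate or sample size is touched. But describing each formulation's safety is one of its two stated objectives, and duration is a listed part of that description.

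For unsolicited AEs nothing else in Table 5.1 would reveal the loss. SAP 4.4.1.1.7 derives an ongoing status for solicited reactions, but the SAP has no counterpart for unsolicited AEs, SAEs or MAAEs.

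**Working it through.** The plan states no duration figure and no expected share of unresolved events, so there is no figure of its own to reproduce. The check has three parts.

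**1. Tracing the rule**

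- *Unsolicited non-serious AEs:* SAP 4.4.1.2.4 applies directly. No stop date means no duration.
- *SAEs:* the same, through SAP 4.4.1.3.3.
- *MAAEs:* by inference. The SAP has no MAAE duration rule. From V01 to V02 they are unsolicited AEs (SAP 4.4.4.5), and the protocol synopsis has later ones recorded as unsolicited AEs in the memory aid.
- *When a stop date counts as absent:* only if none was obtained during the study. The study runs to the telephone contact at D180 (+14 days).

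**2. Direction and rough size, under assumed distributions**

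Assumptions, none from the documents except the D180 cut-off: durations exponential with true mean m, onset uniform over the window shown, and the stop date absent if and only if the event is unresolved at D180. There were 1,000,000 simulated events per cell. Each cell gives the share without a stop date, then the mean of the non-missing durations in days, then its relative error.

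| Event type, onset window | m = 7 | m = 30 | m = 90 | m = 180 |
|---|---|---|---|---|
| Unsolicited AE, D0–D30 | 0.0%; 7.0; 0% | 0.4%; 29.3; −2% | 16.0%; 58.6; −35% | 40.0%; 70.2; −61% |
| SAE, D0–D180 | 3.9%; 6.7; −4% | 16.6%; 24.1; −20% | 43.3%; 42.9; −52% | 63.1%; 50.7; −72% |
| MAAE, D30–D180 | 4.6%; 6.7; −5% | 19.9%; 22.9; −24% | 48.7%; 37.8; −58% | 67.9%; 43.5; −76% |

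The share without a stop date can be checked by hand. For onset uniform on (a, b) it is (m/(b − a)) × [exp(−(180 − b)/m) − exp(−(180 − a)/m)].

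- SAEs, m = 30: (30/180) × [1 − exp(−6)] = 0.1667 × 0.9975 = 0.166.
- Unsolicited AEs, m = 30: (30/30) × [exp(−5) − exp(−6)] = 0.0067 − 0.0025 = 0.004.

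For SAEs with m = 30, the dropped events average 59.5 days and the kept ones 24.1. The two recombine to the true mean: 0.834 × 24.1 + 0.166 × 59.5 = 20.1 + 9.9 = 30.0.

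The dropped events are longer on average, but not in every case. A short event that begins just before last contact is lost too. In the SAE and MAAE scenarios, 3 to 14% of dropped events were shorter than the median of those kept.

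**3. A mixture, purely assumed**

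Suppose a share q of AEs persists to last contact and the rest average 8.5 days. With onset on average at D15 and last contact at D187 (mid-window), the minimum duration of a persistent event is 187 − 15 + 1 = 173 days. The SAP rule gives 8.5 days whatever q is. Counting persistent events to last contact, the mean is at least (1 − q) × 8.5 + q × 173:

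- q = 5%: 8.1 + 8.7 = about 17 days
- q = 10%: 7.7 + 17.3 = about 25 days
- q = 20%: 6.8 + 34.6 = about 41 days

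Nothing in the documents supports any particular q. The example shows only that the reported figure does not respond to q.

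**The case against.** Several counter-arguments have force.

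- **Related events are largely protected.** Their stop dates are actively solicited, and SAP 4.3.1.3.7 adds that AEs likely to be related "that persist at the end of the trial will be followed up by the Investigator until their complete disappearance" or stabilization. All injection-site AEs are related by convention. A reader might infer that a formulation causing persistent events would look better on duration. The documents do not support that: events attributed to vaccine are the ones whose stop dates are pursued. What remains is a related event that stabilises without resolving, and the larger group judged unrelated.
- **Stop dates can arrive after V02.** Because the diary card is collected at V02, a reader might infer that stop dates cease there and that a large share of ordinary AEs would lose their durations. The footnote rules this out, since dates may be supplied throughout the study. The effect on short, early-onset AEs is therefore negligible.
- **Unresolved events stay in the analysis.** They still count in the incidence, intensity and relationship results, and subject listings mark missing data. Outcome is tabulated for SAEs and MAAEs, so non-resolution is visible there. This stands, but it does not correct the duration summary, and unsolicited AEs have no outcome item.
- **Table 5.1 names duration without specifying a statistic.** Classes with a missing or ongoing row would be compatible with the text. That is fair, but the SAP does not require such a row, and its derivation makes the value missing rather than ongoing.
- **Both documents say no replacement or imputation will be done.** Labelling a minimum duration as censored does not invent a stop date, so that principle can stand.

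**Conclusion.** The point holds in a limited form. The SAP discards a known minimum duration for events that it elsewhere calls ongoing, so any duration summary over the non-missing values is biased short. The direction follows from the rule; the size cannot be computed from the documents. Under the assumed exponential model it runs from nil (unsolicited AEs with early onset and a 7-day mean) to −76% (late-onset MAAEs with a 180-day mean). Real events with actively sought stop dates would fare better than the model.

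The effect falls mainly on long-lasting or late-onset events judged unrelated to vaccination. The reach is explicit for unsolicited non-serious AEs and SAEs and inferred for MAAEs. It concerns the completeness of the safety description only. It does not support a claim that events are hidden altogether or that the comparison of formulations is distorted in a known direction.

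**What to change.** In SAP 4.4.1.2.4 and 4.4.1.3.3, and in an explicit rule for MAAEs:

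- If the start date is complete and the stop date is wholly absent, classify the event as ongoing. Derive a minimum duration of last contact date − start date + 1, flagged as censored, and impute no stop date.
- Keep duration missing when the start date is missing or partial, and when the stop date is partial. A partial stop date usually belongs to an event that has resolved, so carrying it to last contact would overstate its length.

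In Table 5.1, for unsolicited AEs, SAEs and MAAEs, report n (%) ongoing at last contact and summarise duration in classes that include an ongoing class. A Kaplan-Meier median is optional in a descriptive study.

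The cost is a short SAP edit, one derived flag and one extra table row. The dates are already collected, and SAP 4.4.4.4 already uses the last contact date.

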4.4.1.3 SAEs

4.4.1.3.1 Last Vaccination

Not applicable, as there is only one vaccination.

4.4.1.3.2 Time of Onset

Time of onset will be computed using the same methodology than for unsolicited non-serious AEs described in [Section 4.4.1.2.3](#).

SAEs will be analyzed throughout the study using the following periods:

- Within 7 days after vaccine injection
- Within 30 days after vaccine injection
- During the 6-month follow-up period (i.e., from V02 until the last subject contact)
- During the study (i.e., all SAEs occurred during the study)

An SAE with missing time of onset will be considered to have occurred just after the vaccination indicated by the visit number, so will be included in these tables.

Note: SAEs that occurred before vaccination (negative time of onset) will not be included in analysis, but will be listed separately.

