§§This call to be made 8 to 10 days after the vaccination at V01. If D8 (+3 days) falls on a weekend or a holiday, the telephone call may be made on the following working day. During this call the staff will determine whether the subject experienced any SAE, Grade 3 solicited adverse reactions (including ELS) not yet reported, remind the subject or subject's parent/guardian to continue to use the DC up to V02 and to bring the DC to the study center at V02, and will confirm the date and time of V02.

***The MA is used for recording any AEs between V02 and TC2.

†††An MAAE that occurs between V01 and V02 will be recorded as unsolicited AEs.

‡‡‡Staff will contact the subject or subject's parent/guardian by telephone at 180 days (+14 days) after vaccination at V01 to identify the occurrence of any MAAEs and unreported SAEs for the period between V02 and TC2.

4 Endpoints and Assessment Methods

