4.4.1.2.3 Time of Onset

Time of onset is derived from the start date of the unsolicited non-serious AE provided in the clinical database and the date of last vaccination:

- start date of the unsolicited non-serious AE minus date of previous vaccination

The time of onset should be considered as missing only if one or both of the dates are missing or partially missing.

The unsolicited non-serious AEs will be analyzed “Within 30 days”, which corresponds to AEs with a time of onset between 0 and 30 days after vaccination or missing. An AE with missing time of onset will be considered to have occurred just after the vaccination indicated by the visit number, so will be included in these tables.

Note: Unsolicited non-serious AE that occurred before vaccination (negative time of onset) or with a time of onset will not be included in analysis, but will be listed separately.

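### SAP 4.4.1.3.2 disagrees with SAP 5.3.1.5 and Table 5.1 on where an SAE without a full onset date is counted, and on whether SAE follow-up starts at V02 or D31

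*SAP*

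**What the plan says.** **Missing or partial onset.** SAP 4.4.1.3.2 takes the SAE onset method from 4.4.1.2.3 (unsolicited non-serious AEs). There, "The time of onset should be considered as missing only if one or both of the dates are missing or partially missing", so a start date with only month and year has a missing onset. For such an SAE, 4.4.1.3.2 states: "An SAE with missing time of onset will be considered to have occurred just after the vaccination indicated by the visit number", and the event goes into the period tables. SAP 5.3.1.5 says otherwise: "Since SAEs are not collected by visit, though missing or partially missing start dates will not be imputed, logic will be applied". The outcome is one of two periods, D0-D30 or D31 onward. The logic is not described, and the 7-day period is not mentioned.

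**Start of SAE follow-up.** SAP 4.4.1.3.2 lists four periods: within 7 days, within 30 days, the 6-month follow-up, and the whole study. It defines the third as "During the 6-month follow-up period (i.e., from V02 until the last subject contact". The SAE row of Table 5.1 (SAP 5.1.3.2.2) has instead "From D31 to 6-month follow-up contact for all subjects", and 5.3.1.5 also uses D31. The MAAE row of the same table has "From V02 to 6-month follow-up contact for all subjects".

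**Timing of V02.** SAP 3.1 places V02 at D30 to D44. Table 3.2 narrows the window to +7 days (D30-D37) for the CMI subset.

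**The concern.** The onset rule in 4.4.1.3.2 needs a visit number that 5.3.1.5 says SAEs do not have. The two rules can also send the same event to different periods. Take an SAE about four months after vaccination with only month and year known. Under 4.4.1.3.2 it sits just after vaccination, in the 7-day and 30-day rows. Under 5.3.1.5 it can be assigned to D31 onward. Such a case can arise, because the D180 call is made "to identify the occurrence of any MAAEs and unreported SAEs for the period between V02 and TC2", so some dates may rest on recall.

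Separately, V02 and D31 are different days for most permitted visit dates. With a V02 start, an SAE between D31 and the day before V02 is in neither the 30-day row nor the follow-up row.

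At stake is whether two programmers working from different sections would get the same 7-day, 30-day and follow-up SAE counts by study group. Describing the safety profile of each formulation is one of the two trial objectives. Where SAEs are few, moving one event is visible.

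**Working it through.** The plan gives no figure to reproduce here. The check is a day count, followed by an illustrative size.

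**1. Days in neither row or in both.** The 30-day row covers onset days 0-30. If follow-up starts at V02, the days in neither row are D31 to V02 - 1, so gap = max(0, V02 - 31).

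| V02 on | In neither row | In both rows |
|---|---|---|
| D30 | 0 | D30 |
| D31 | 0 | none |
| D34 | 3 (D31-D33) | none |
| D37 (end of CMI window) | 6 (D31-D36) | none |
| D44 (end of window) | 13 (D31-D43) | none |

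If follow-up starts at D31, there is no gap and no overlap for any V02 date. With a V02 start, a visit after D44 gives a gap above 13 days, and a missed visit leaves no start date. So 13 days is the limit only for visits in window.

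**2. Average gap, under assumed V02 dates.**
- V02 uniform on D30-D37 for everyone: (0+0+1+2+3+4+5+6)/8 = 21/8 = 2.625 days.
- V02 uniform on D30-D44: (0+0+1+...+13)/15 = 91/15 = 6.067 days.
- Each subject uniform over their own window: the CMI subset is 36 + 60 + 60 = 156 (Protocol 5.1.1), leaving 1350 - 156 = 1194. The mean is (1194 × 6.067 + 156 × 2.625)/1350 = 5.67 days.
- Everyone on the last day of their window: (1194 × 13 + 156 × 6)/1350 = 12.19 days.

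**3. Expected SAEs in the gap.** The documents give no SAE incidence. I assume 1% to 4% over six months, with onset uniform over the 181 days D0-D180. Expected number = n × incidence × gap/181, with n = 1350 overall and 225 per study group. P(at least one in a group) = 1 - exp(-expected number per group).

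| Mean gap | Overall | Per study group | P(at least one in a group) |
|---|---|---|---|
| 2.625 days | 0.20-0.78 | 0.033-0.131 | 3.2-12.2% |
| 5.67 days | 0.42-1.69 | 0.070-0.282 | 6.8-24.6% |

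For example, 1350 × 0.04 × 5.67/181 = 1.69. With every V02 on the last window day the figures are 0.91-3.64 overall and 0.15-0.61 per group. None of these includes late or missed visits.

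**4. What a known month tells you.** I took every vaccination date in each planned inclusion period (Protocol 5.1.5, whole calendar months) and every onset day from D31 to D180, all equally likely. I then asked whether the calendar month of onset overlaps the early period at all. In all three age cohorts the month alone rules out D0-D7 in 99.4-99.5% of cases and D0-D30 in about 90.1%. The visit-number rule would discard that information. The documents give no frequency of incompletely dated SAEs, so I give no count for this part.

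**The case against.** On dates, SAP 5.3.1.5 is the section dedicated to missing start dates. It separates SAEs from unsolicited AEs and gives the reason. The sentence in 4.4.1.3.2 nearly repeats the non-serious AE wording and reads as carried over; a programmer could hardly apply a visit number that does not exist. This stands: 5.3.1.5 is the more natural text to follow. It does not close the matter, because its logic is undefined and it is silent on the 7-day row, which both 4.4.1.3.2 and Table 5.1 require.

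On the boundary, Table 5.1 and 5.3.1.5 agree on D31, and only a parenthesis in 4.4.1.3.2 says V02, perhaps as shorthand for the nominal D30. That is a fair reading, but V02 has a defined window, and the MAAE row of Table 5.1 uses V02 where the SAE row uses D31.

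On size, no hypothesis is tested, and the 24-hour reporting rule in Protocol 10.1 should keep poorly dated SAEs few. Both points stand.

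A reader might infer that some SAEs drop out of the report, or that the comparison of formulations is materially distorted. The documents do not support either. SAP 4.4.1.3.2 and 5.1.3.2.2 both provide for all SAEs from D0 to the end of follow-up, and that table is the same under either text. Nor do the documents show that the 4.4.1.3.2 sentence is the one that would be programmed.

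**Conclusion.** Both conflicts are in the current SAP text, and neither comes from redaction or a broken table. Followed as written, 4.4.1.3.2 puts late, partly dated SAEs in the early rows. With V02 in window it also leaves 0 to 13 days (0 to 6 in the CMI subset) outside both the 30-day and follow-up rows, or counts D30 in both if V02 is on D30.

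The impact is minor and confined to descriptive sub-period SAE rows. The day counts follow from the documents alone. Every expected count rests on the assumed incidence, uniform SAE timing and assumed V02 dates. Under the two spread-out V02 patterns it is well below one SAE per study group. It is worth correcting because the same data should give one answer and the correction is nearly free.

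**What to change.** In SAP 4.4.1.3.2:
- Define the third period as D31 to last contact, matching Table 5.1 and 5.3.1.5.
- Delete the visit-number sentence for SAEs and refer to 5.3.1.5.

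In SAP 5.3.1.5, write out the logic:
- The known part of the start date decides between D0-D30 and D31 onward.
- An SAE is excluded from the 7-day row when the known part rules out D0-D7.
- One pre-specified default, chosen by the sponsor, applies to every date that stays ambiguous, including D0-D7 versus D8-D30. Compatibility with D0-D7 alone does not settle that case.

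Footnote the SAE tables with the number of events placed by the default, and footnote that MAAE follow-up starts at V02 while SAE follow-up starts at D31.

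The cost is a few SAP sentences and two table footnotes. No new data are needed and no study procedure changes.
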